WatchPAT: During the hospital overnight stay, trained study staff will place the WatchPAT sleep monitor. The primary measures will be for oxygen saturation and apnea hypopnea index (AHI). Each participant will wear the watch with a one-time use finger cuff as recommended by the FDA. The watch will be placed by 8 PM, and will be removed the following morning.

The following morning, a blood sample for baseline metabolic labs will be drawn and infusion studies with the modified OGTT will be completed.

Study Drug Injections Exenatide (Byetta):

[figure not shown]
A subset of 10 untreated girls with PCOS who are receiving the overnight Acetate infusion will be administered two injections of Exenatide (Byetta) (5 mcg) during the in-patient admission for the OGTT. The first injection will be administered the night of admission at 6:30-7 PM. 30 minutes prior to the study diet containing a fixed macronutrient distribution listed below. The subject will be monitored throughout the night by nursing staff. The second injection will be administered at approximately 8 AM, 30 minutes prior to the OGTT load of 75 grams glucose. Following the second injection, study staff and CTRC nursing staff will be bedside for the remainder of the patient's inpatient admission at CHCO. Blood glucose measurements will be taken regularly for 6 hours post OGTT.

Details of Stable Isotope Tracer studies with an OGTT: After the overnight fast, subjects will consume a 75 grams glucose load with an additional 25 grams of fructose to stimulate hepatic de novo lipogenesis, and a ¹C₁₃ glucose tracer (40 mg/kg) to calculate the rate of appearance of exogenous glucose²¹.

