The stable isotope method to be utilized is an OGTT with IV glucose and glycerol stable isotope tracers in all subjects, and acetate tracers in select subjects, based on power analysis and cost. For the glucose and glycerol tracers, we will utilize the tracer doses as in our previous hyperinsulinemic clamp studies, as these rates successfully detected basal and stimulated glucose and glycerol Ra. Whole-body lipolysis will be measured under basal conditions and during the OGTT (75 grams glucose + 25 grams fructose + ¹C₁₃ tracer), using a primed (1.6 μ mol/kg), constant (0.11 μ mol/kg/min) infusion of ²H₅glycerol⁴⁷. Hepatic IR will be measured under basal conditions and during the OGTT, using a primed (4.5 mg/kg), constant (0.03 mg/kg/min) infusion of 6,6-²H₂glucose⁴⁸. Blood sampling will continue for 6 hours post-OG to allow return to baseline, based on our pilot data shown in Figure 2 that 2 hours is inadequate. Blood for tracer analysis and glucose and insulin concentrations will be drawn at baseline, every 10 min during the last 40 min of the basal period, and every 15 min post OG load.

The rate of the acetate tracer will be 2 μ mol/kg/min with no prime, based on previous studies⁴⁹. The oral challenge study design is shown in Figure 4. Hepatic De Novo lipogenesis will be measured in the fasting state, and in the fed state following the glucose load, by analyzing the incorporation of the C₁₃ tracer into hepatically secreted lipids such as 16 and 18 carbon long chain

Figure 4: Proposed Oral Glucose Challenge

fatty acids in VLDL⁴⁹. Blood will be drawn at baseline and for the last 4 hours of the basal state and the postprandial state.

A total of 40 girls will receive the overnight acetate infusion. This total will be broken down into 20 un-treated PCOS patients (10 without Byetta and 10 with Byetta), 10 obese control patients and 10 from PCOS patients treated with Metformin or OCP (5 from each group). Analysis of $^2\text{H}_5\text{glycerol}$, 6,6- $^2\text{H}_2$ and long chain fatty acid incorporation of $^2\text{C}_{13}$ Acetate, will be performed by our collaborator [name], using a modification of the negative ion chemical ionization gas chromatography mass spectrometry as in our previous studies^{49,50}.

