Justification/Minimization: GLP-1 receptor agonists such as exenatide (Byetta) aid in secretion of insulin and suppress the action of glucagon. Our preliminary data show increased glucose concentrations secondary to relative inadequate insulin secretion following an oral glucose load in adolescent girls with PCOS compared to their obese control counterparts. Participants in this overnight study will only receive 2 doses of this short acting medication, and the well tolerated lower risk 5 mcg dose. They will be monitored at CHCO inpatient following the first injection of 5 mcg of Byetta. Patient will be monitored for excessive vomiting and dehydration overnight. Vital signs will be taken overnight every 4 hours by clinical inpatient nurses per CHCO overnight nursing policy. The patient will be instructed to alert the night nursing staff if any nausea or dehydration occurs overnight and study staff will be notified. During the study day (visit 3), study staff and CTRE nursing staff will be bedside monitoring patient from 6AM to 2PM periodically taken vital signs and assessing signs of excessive vomiting and dehydration. Glucometer readings will be taken at regular intervals for 6 hours after the OGTT to measure blood glucose concentrations. Study staff and research nursing will continuously monitor patient until discharge from hospital. At the time of discharge, the half-life of Byetta will have expired.

21. Violation of Privacy and Loss of Confidentiality

Description: These are both risks to which research participants are exposed. The possibility of these risks increases when protected health information is collected. Every effort will be made to decrease this risk by limiting access to protected health information, storing this information in a password protected database, and identifying subjects only by a unique identifier that is kept in a separate location in a locked container, traceable only by study personnel. All of the tests involve the risk of identifying asymptomatic abnormalities. The study may include risks that are unknown at this time.

Justification/Minimization: Every effort will be made to decrease the risk of loss of confidentiality by limiting access to protected health information, storing this information in a password protected database, and de-identifying study specimens.

E. Benefits of the study:

Benefits to Society:

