If a subject experiences any of the following, the subject will be withdrawn from the study.

1. Inability to complete study procedures
2. Abnormal screening labs (LFT's >4 times elevate, HbA1C>6.4%, Hg <9 mg/dL)
3. Subject becomes pregnant during study

D. Protocol Stopping Criteria

If one or more subjects experience any of the SAE's listed above, the PI will consult with the mentor prior to continuing study visits with subjects. The mentor and RSA will consult about the significance of the SAE's and make a recommendation to the PI.

VII. Data Analysis Plan:

Statistical Plan for Method Development: The previously described tracer protocol and mathematical modeling with any refinements will be performed in an additional 9 subjects. Outcome measures (raw suppressed glucose and glycerol Ra, insulin concentration required for 50 percent of peak suppression and percent suppression of basal Ra) will be compared between the OG subjects and a matched cohort of girls who have undergone hyperinsulinemic euglycemic clamps with identical glucose and glycerol tracer infusion rates. Subjects in the two groups will be matched on PCOS diagnosis, race, percent body fat, percent liver fat, and time post-menarche. An equivalence design will be used to compare the outcomes in the two groups and to demonstrate whether there are clinically significant differences in outcomes from the OG model and the hyperinsulinemic clamp. For purposes of sample size calculation, we used estimates from the investigator's pilot study. Using an equivalence limit of one standard deviation for each outcome measure (SD=50 units for glycerol IC50 and SD=39 units for glucose IC50) and a correlation of 0.2 between outcomes on matched subjects, 15 matched pairs gives 80% power to demonstrate equivalence. 70 girls have completed the hyperinsulinemic euglycemic clamps, so adequate matching will be possible.

Overall Project Statistical Plan:

Power calculation: The primary outcome is hepatic IR measured as IC₅₀ glucose Ra. Using our preliminary data, a two-tailed t-test and an alpha of 0.05, completing 13 controls and 32 PCOS provides 86% power to detect a difference of 35 IU/L in the insulin concentration.

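### In the 10 exenatide girls the basal sampling window straddles the second injection, so their basal reference mixes two drug states

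*Combined protocol and SAP*

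**What the plan says.** All references are to the combined protocol and SAP.

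- **Sampling.** Section III.C, Visit 3, Details of Stable Isotope Tracer studies with an OGTT, plans an "OGTT with IV glucose and glycerol stable isotope tracers in all subjects". Blood for tracer, glucose and insulin is drawn at baseline, "every 10 min during the last 40 min of the basal period", "and every 15 min post OG load". The text gives no gap between the basal period and the load. It refers to Figure 4 for the design, and that figure is not available here.
- **Dosing.** The Visit 3 paragraph on exenatide concerns "A subset of 10 untreated girls with PCOS who are receiving the overnight Acetate infusion". It states: "The first injection will be administered the night of admission at 6:30-7 PM". It then states: "The second injection will be administered at approximately 8 AM, 30 minutes prior to the OGTT load of 75 grams glucose".
- **Mechanism.** Section III.D, item 20, says that drugs of this class "aid in secretion of insulin and suppress the action of glucagon". The Visit 3 laboratory table lists insulin as a determinant of hepatic and adipose insulin resistance, and glucagon as an influence on hepatic insulin resistance.
- **Use of the basal value.** Section VII, Statistical Plan for Method Development, names "percent suppression of basal Ra" and the insulin concentration at half of peak suppression as outcomes. The primary outcome in section III.A is the IC50 for glucose Ra. The tracer text treats the basal state as a measurement condition for hepatic insulin resistance.
- **Handling of this subset.** No visible text moves the basal window for these 10 girls, says which of their samples form the reference, or says whether they enter the pooled PCOS analysis.

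**The concern.** A basal reference should describe one physiological state. Here a dose that the protocol expects to act on insulin and glucagon falls inside the window that supplies the reference. If Ra begins to fall before the drink, part of the drug's effect is counted as baseline. Percent suppression then reads low, and the Ra level that marks 50% suppression moves. The other groups have no injection in their window, so the same named quantity would be measured under different conditions in one subset.

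The values are used in two places. Aim 3 and section VII relate hepatic de novo lipogenesis (HDNL) to hepatic and adipose insulin resistance. These girls are 10 of the 40 who receive acetate according to the Visit 3 text (the enrollment table gives 50). They also sit in the PCOS row of the enrollment table (10 of 50), and section VII does not exclude them from the PCOS-control comparison of IC50.

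**Working it through.** **1. Timeline.** Take the drink as time 0, at about 8:30 AM. The second injection is then at about -30 min (8:00 AM). If the basal period ends at the drink, the draws fall at -40, -30, -20, -10 and 0. The window opens at about 7:50 AM. That is 12 h 50 min to 13 h 20 min after the evening injection at 6:30-7 PM, so every basal draw follows one dose.

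**2. Draws after the second injection.**

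| Reading of the basal draws | Strictly after -30 min |
|---|---|
| Five draws, -40 to 0 | 3 of 5 (4 of 5 if the -30 draw follows the injection) |
| Five draws plus the separate baseline draw | 3 of 6 |
| Four draws, -40 to -10 | 2 of 4 |
| Four draws, -30 to 0 | 3 of 4 |

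Half or more follow the injection on each reading. With five draws, an actual injection time from -40 to -25 min leaves 3 or 4 of 5 after it, and an injection at -20 min leaves 2 of 5. The Steele equation in section VII works on pairs of draws, and 3 of the 4 pairs (-30 to -20, -20 to -10, -10 to 0) lie wholly after the injection.

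**3. Effect on percent suppression.** The documents do not say how far or how fast Ra falls after the injection, so this is an illustration. Let s be suppression against a reference taken before the second injection, w the share of the reference taken after it, and d the assumed fall in Ra in that share. Hold the post-drink nadir fixed. Then

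observed suppression = 1 - (1 - s)/(1 - w·d).

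With s = 0.70:

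| d | w = 3/6 | w = 3/5 | w = 3/4 (Steele pairs) |
|---|---|---|---|
| 0.05 | 1 - 0.30/0.975 = 69.2% | 1 - 0.30/0.97 = 69.1% | 1 - 0.30/0.9625 = 68.8% |
| 0.20 | 1 - 0.30/0.90 = 66.7% | 1 - 0.30/0.88 = 65.9% | 1 - 0.30/0.85 = 64.7% |

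**4. Effect on the 50% point.** Set the reference Ra to 1.00 and the nadir to 0.30. Half of peak suppression is reached at (1.00 + 0.30)/2 = 0.65. With w = 3/5 the target becomes (0.97 + 0.30)/2 = 0.635 for d = 0.05, and (0.88 + 0.30)/2 = 0.59 for d = 0.20. If 50% means half of basal Ra, the target goes from 0.50 to 0.485 or 0.44. A lower target would call for more insulin, so IC50 may read higher. The documents give no insulin-Ra curve, so the change in IC50 cannot be computed.

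**5. HDNL itself.** Its basal blood covers the last 4 hours. Only the last 30 min of that, 30/240 = 12.5%, follows the second injection.

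**The case against.** The strongest reply has four parts.

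- **The figure may settle it.** That the window ends at the drink is inferred from the sampling sentence, and Figure 4 might show otherwise. This stands as a caveat. If the basal period ends at the injection, no draw is affected and one added sentence in the text closes the point.
- **The subset exists for HDNL.** A reader might infer that a planned exenatide-versus-untreated comparison of Ra or insulin sensitivity is biased. The documents do not support that. Aim 2 names only metformin and oral contraceptives, GLP-1 agonists appear only in Aim 3 for their effect on HDNL, and section VII specifies no such contrast. Percent suppression is listed only among the method-development outcomes. What remains is the indirect route through the HDNL correlations and the pooled PCOS group.
- **There is no drug-free baseline to lose.** A reader might take the -40 min draw as untouched by drug. It is not, because the evening dose comes before it. Item 20 calls the drug short acting, so carry-over may be small, but the documents do not quantify it. Sampling before the second injection gives one consistent state, not the never-dosed state of the other groups.
- **Other basal inputs may come from elsewhere.** A reader might infer that basal insulin in the minimal model and fasting insulin in the disposition index are affected too. The plan does not say which draw supplies them. The separate baseline draw or the morning metabolic sample could do so. Nor does it say that basal Ra is a five-draw mean.

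None of this tells the analyst which draws to use in these girls.

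**Conclusion.** The point holds in a limited form. On the plain reading, half or more of the basal draws in 10 girls follow the second injection, and the plan defines no reference that avoids mixing the two states. The expected direction, from the protocol's own account of the drug, is a basal Ra and a percent suppression that read too low, with a possible shift in IC50. The size is unknown. The illustrated loss of roughly 1 to 4 percentage points from 70% (up to about 5 if Steele pairs are averaged) rests on an assumed 5-20% fall within 30 min and on an unchanged nadir. The conclusion also assumes that the basal period ends at the drink and that these girls stay in the PCOS group and the HDNL correlations. It does not show that the primary comparison is materially biased. The correction is specific and cheap, so it should be made.

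**What to change.** Reconcile the exenatide and tracer-sampling paragraphs of Visit 3, leaving the injection as it is.

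1. For this subset, define basal Ra, basal insulin and the resting metabolic-cart value from measurements completed before the second injection.
2. One way is to move four of the five draws to before the injection and keep one at time 0. The number of draws and the blood volume do not change, and the first post-load Steele interval stays at 15 min (0 to +15). Moving all five would stretch that interval to 45 min (-30 to +15) and leave no immediate pre-load value.
3. Label samples between injection and drink as post-dose.
4. For girls already studied, use the baseline and -40 draws, and the -30 draw if it was taken before the injection.
5. State whether these girls enter the pooled PCOS group, and report the IC50 and HDNL-insulin-resistance analyses with and without them.

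**Cost.** For girls still to be studied, sampling starts earlier and the glucose and glycerol infusions may have to as well; the visible text does not give their start time. For girls already studied, the basal value is noisier. With independent, equally variable draws, a mean of 2 instead of 5 has a standard error √(5/2) = 1.58 times as large, and a mean of 3 has √(5/3) = 1.29 times. If the baseline draw precedes the tracer infusion it can supply insulin and glucose but not Ra, and basal Ra may then rest on a single Steele pair (-40 to -30).

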Obese adolescents are at risk of T2D and its complications, reduced exercise capacity, increased liver and visceral fat, muscle dysfunction and cardiovascular dysfunction therefore the tests performed screening for each of these problems provide useful information to these subjects. Likewise, sedentary subjects of any weight are at increased risk of reduced bone mineral density (BMD), T2D, reduced exercise capacity, increased liver and visceral fat, muscle dysfunction and cardiovascular dysfunction. Therefore, all of the subjects may benefit from the results of DEXA, glucose testing and exercise prescription and dietary counseling.

C. Study Design and Research Methods

Study Calendar	Visit 1 – Screen	Visit 2 –MRI	Visit 3 – Overnight
Consenting and Eligibility Assessment	X		
History & Physical	X		
Intravenous Blood Draw	X		X
Finger Stick Blood Draw		X	
Urine Pregnancy Test			X
Accelerometer Teaching	X		
Gut Bacteria Collection			X
Questionnaires- SEARCH Food frequency, Activity 3DPAR, Strengths and Difficulties, a sleep diary, and Sleep assessments			X
Sleep Study with salivary melatonin collection (pending scheduling)			X
WatchPAT sleep study			X
DEXA Scan			X
Glucose, Glycerol and Acetate Tracers			X
Study Drug (Byetta) GLP-1 Injection			X
EndoPat and Dynapulse		X	
MRI of abdomen and liver, P MRS of Liver		X	
Metabolic Cart			X
Total Time of visit (approximately)	3 Hours	2 Hours	24 Hours
Location of Visit	CHCO CTRC Outpatient	UCD Outpatient Brain Imaging Center	CHCO Inpatient Hospital

The study consists of 3 visits - 2 outpatient visits and one overnight inpatient visit. Inpatient visit will last approximately 24 hours, outpatient screening visit approximately 3 hours, outpatient MRI visit approximately 2 hours. The 3 visits would be completed within 4 months time.

Overall enrollment procedure plan per group

Test Group	Screening	MRI/MRS	Overnight stay	Glucose and Glycerol tracers	DEXA	Overnight acetate tracer	GLP-1 Injection (Byetta)
PCOS	40-50	50	50	50	50	30	10
PCOS w/ Metformin	10-13	10	10	10	10	5	0
PCOS w/ OCP's	10-12	10	10	10	10	5	0
Obese	20-30	20	20	20	20	10	0
Total	Up to 105	90	90	90	90	50	10

VISIT 1 (SCREEN VISIT)

Pediatric CTRC Outpatient unit: Participants will begin with a medical screening and physical exam. During this visit, patients will review and complete consent documents, have demographics

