Minimizing Risk: Certain studies at our institution draw over 7ml/kg in 6 weeks, or up to 7 ml/kg in a single draw, but include iron supplementation. Otherwise, the routine guidelines in our Pediatric CTRC are 2.5ml/kg for a single draw and no more than 5ml/kg over a 4 week period. Our baseline visit will include 11.5 ml of blood (HbA1c, Hb, Cr, AST, ALT) and 25.5 ml of blood for PCOS patients (additional draw for T4, TSH, prolactin, LH, FSH, 17OH progesterone and DHEAS). The OGTT visit includes 207.5 ml of blood which will occur within 4 weeks of the initial visit. Thus, our OGTT visit is within the NIH Clinical Center guidelines of 9ml/kg in 6-8 weeks and within Children's Hospital Colorado's institutional guidelines of 5 ml/kg. In addition, by study design, subjects are screened by our baseline CBC and excluded if anemic, further increasing the safety of the study regarding blood draws. We will use a minimum weight cutoff of 38 kg to remain below the most conservative pediatric CTRC blood drawing guidelines. In addition, we pre-screen subjects with a hemoglobin and hematocrit at their baseline visit, and exclude subjects with anemia. This screening also helps to increase the safety of the blood draw. In addition, the blood planned to be frozen and held could also be omitted if needed to reduce blood volume for a particular subject. Finally, our CTRC has a system to track other studies subjects might enroll in, and we ask during our consent process if the subject has been involved in any other studies in the past 6 weeks to avoid excessive blood drawing.

Justification: Screening laboratory measurements are necessary to assure that patients meet inclusion/exclusion criteria before any further study is completed. A CBC is necessary as a

screening lab, to rule out anemia. A hemoglobin A1c can be used to rule out diabetes. Hormone levels of free and total testosterone, and sex hormone binding globulin are needed to categorize patients as having PCOS, and prolactin, DHEAS, LH, FSH, TSH, total T4 or 17-OH progesterone to rule out other causes of oligomenorrhea, if not done previously.

2. IV Risks

Description: Two peripheral IV's will be placed during the OGTT. One will be to infuse the isotopes, and the other will be for drawing blood samples.

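### At the 38 kg weight floor, the stated OGTT blood volume is 5.46 mL/kg, above the 5 mL/kg four-week guideline that the floor is meant to respect

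*Combined protocol and SAP*

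**What the plan says.** Everything needed is in the risk-minimisation text of Section III.D.1 (Blood Sampling). The routine pediatric CTRC guidelines are 2.5 mL/kg for a single draw and "no more than 5ml/kg over a 4 week period". On volume and timing, the section states: "The OGTT visit includes 207.5 ml of blood which will occur within 4 weeks of the initial visit". Screening takes 11.5 mL, or "25.5 ml of blood for PCOS patients" when the additional diagnostic tests are drawn.

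The section then says, with no condition on weight, that the OGTT visit complies with the "NIH Clinical Center guidelines of 9ml/kg in 6-8 weeks" and with the hospital's "institutional guidelines of 5 ml/kg". The weight floor follows: "We will use a minimum weight cutoff of 38 kg to remain below the most conservative pediatric CTRC blood drawing guidelines". Among the further safeguards, it notes that "the blood planned to be frozen and held could also be omitted if needed to reduce blood volume for a particular subject".

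Two other places bear on this. Section III.C gives a looser timetable for the study as a whole: "The 3 visits would be completed within 4 months time". The eligibility criteria in Section III.B contain no lower weight limit; their only absolute weight limit is the upper one of 300 lb.

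**The concern.** A weight floor chosen to satisfy a mL/kg guideline should equal the planned volume divided by that guideline, or be higher. Here 207.5 mL divided by 5 mL/kg is more than 38 kg, before any screening blood is counted. If so, both the floor and the unconditional 5 mL/kg compliance statement fail for the lightest girls the protocol would accept.

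The stake is participant safety. Many participants will be minors, and the protocol itself lists excessive blood volume as a risk of the procedure. The floor is one of several protections, alongside exclusion for anemia, optional omission of stored blood and tracking of other studies, so an error in it weakens the set without removing it. No efficacy analysis depends on it.

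**Working it through.** **Inputs, all from Section III.D.1.** Floor 38 kg; guideline 5 mL/kg over four weeks; OGTT visit 207.5 mL; screening 11.5 mL, or 25.5 mL for PCOS with the extra labs; NIH figure 9 mL/kg.

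**Step 1: try to reproduce 38 kg.** Minimum weight = volume ÷ guideline. For the OGTT visit alone:
- at 5 mL/kg: 207.5 ÷ 5 = 41.5 kg
- at 2.5 mL/kg: 207.5 ÷ 2.5 = 83.0 kg
- at 7 mL/kg (mentioned for other studies): 207.5 ÷ 7 = 29.6 kg
- at 9 mL/kg: 207.5 ÷ 9 = 23.1 kg

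Adding screening blood of 11.5, 25.5 or 37 mL gives 43.8 to 48.9 kg at 5 mL/kg, 87.6 to 97.8 kg at 2.5, 31.3 to 34.9 kg at 7, and 24.3 to 27.2 kg at 9. None of these is 38 kg. Working backwards, 38 kg at 5 mL/kg corresponds to 190 mL, a volume the protocol does not state.

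**Step 2: position at the floor.** The allowance is 38 × 5 = 190 mL. Excess = volume − 190; break-even weight = volume ÷ 5.

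| Blood counted in the four weeks | Volume (mL) | mL/kg at 38 kg | Excess over 190 mL | Break-even weight (kg) |
|---|---|---|---|---|
| OGTT visit only | 207.5 | 5.46 | 17.5 (9.2%) | 41.5 |
| plus basic screening, 11.5 | 219.0 | 5.76 | 29.0 (15.3%) | 43.8 |
| plus PCOS screening, 25.5 as the whole draw | 233.0 | 6.13 | 43.0 (22.6%) | 46.6 |
| plus PCOS screening, 25.5 on top of 11.5 | 244.5 | 6.43 | 54.5 (28.7%) | 48.9 |

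The first row applies if screening falls outside the four weeks, which the four-month timetable permits. The second covers controls, and girls with PCOS whose work-up is already complete, when screening falls inside the four weeks as Section III.D.1 says. The third and fourth apply only to girls with PCOS who need the extra labs. The third is the more natural reading of the 25.5 mL; the fourth is an upper bound.

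**Step 3: how much omission would be needed.** Share of the OGTT volume to drop at 38 kg = excess ÷ 207.5: 8.4%, 14.0%, 20.7% and 26.3% for the four rows. The OGTT labs table in Section III.C lists stored samples, but no volume is given for them.

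**Step 4: the NIH figure.** 38 × 9 = 342 mL, above every total in the table. That half of the compliance statement is correct.

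**The case against.** The strongest reply is that the same paragraph already provides a remedy. Stored blood may be left out for a particular girl, and for the OGTT visit alone only 17.5 mL needs to go. On that view the plan merely fails to demonstrate compliance. This stands in part: omission might cure the excess. But it is optional, with no stated volume and no trigger, so it does not make the floor or the compliance sentence correct as written.

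Second, the 5 mL/kg figure is a routine guideline, and the section mentions other local studies that draw about 7 mL/kg. Those studies give iron supplements, which this protocol does not describe, and the protocol itself claims to meet 5 mL/kg.

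Third, the affected weight range may be almost empty. Entry requires age 12 or over, BMI at or above the 90th percentile and, for PCOS, at least 1.5 years since menarche. If one assumes an entry BMI of 22 to 28 (the documents give no cut-point), a girl of 41.5 kg would be between √(41.5/22) = 1.37 m and √(41.5/28) = 1.22 m tall. This stands, and it is why the point is minor. It does not correct a threshold that exists for the lightest participant.

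Fourth, the larger excesses are conditional on timing, on needing the extra labs and on how the 25.5 mL is read. That is fair. Only the 17.5 mL excess needs nothing beyond the stated OGTT volume.

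Finally, one could ask why 5 mL/kg is the benchmark when 2.5 mL/kg for a single draw is stricter. It is used here because the compliance sentence uses it; the stricter figure only widens the gap.

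**Conclusion.** The concern holds, at minor severity. At 38 kg the stated OGTT volume exceeds the four-week guideline by 17.5 mL, and the 5 mL/kg compliance statement is untrue from 38 kg to just under 41.5 kg. With screening blood in the same four weeks, the excess at the floor is 29 mL, or 43 mL for girls with PCOS who need the extra labs (54.5 mL if the two screening figures add).

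This assumes that 207.5 mL is drawn from every girl. The protocol does not say whether that figure is a maximum that includes acetate sampling, which only some girls have (40 in the Visit 3 text, 50 of 90 in the enrollment table of Section III.C). If it is, girls without acetate would meet the guideline at 38 kg only if acetate sampling accounts for at least the excess in their row of the table; girls with acetate would still exceed it. The documents give no weight distribution, so the number of girls affected cannot be computed.

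**What to change.** Keep the 38 kg floor, but make 5 mL/kg a mandatory cap on total blood drawn in any four weeks, with stored samples dropped first. At 38 kg this leaves, for the OGTT visit:
- 190 mL if screening is outside the four weeks
- 190 − 11.5 = 178.5 mL after basic screening
- 190 − 25.5 = 164.5 mL after the PCOS labs (190 − 37 = 153 mL if the two screening figures add)

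Correct the compliance sentence so that the 5 mL/kg claim depends on the cap. It would help to state the stored-sample volume, whether 25.5 mL includes the 11.5 mL, and whether 207.5 mL includes acetate sampling. Only if stored samples cannot cover the excess should the floor rise, to the planned four-week volume for the girl's group divided by 5. List whichever floor is used in the eligibility criteria of Section III.B.

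The cost is a short text amendment and the loss of some stored samples that the protocol already treats as dispensable. If a higher floor proves necessary, it would probably exclude very few girls.
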